7.4.4 Collection of fresh biopsy samples

Collection of serial tumour biopsies will be encouraged during the study. For patients with accessible tumours where patients' consent has been obtained, a fresh tumour biopsy prior to first dose, following ceralasertib and olaparib treatment (on Cycle 1 Day 7), and following progression will be analyzed for downstream effects on ATR pathway that may include but are not limited to biomarkers [CCI], [CCI], [CCI]. On-treatment biopsy timing may be refined with emerging pharmacokinetic and/or pharmacodynamic data during the course of the trial. Accessible lesions are defined as tumour lesions which are amenable to repeat biopsy, unless clinically contraindicated or the patient has withdrawn consent. Failure to obtain sufficient tumour sample after making best efforts to biopsy the tumour will not be considered a protocol deviation.

Details of sample collection, processing, shipping and storage are described in the Laboratory Manual.

7.4.5 [CCI]

[CCI]

[Redacted]

Details on processes for collection and shipment and destruction of these samples can be found in [CCI] or in the Laboratory Manual.

7.5 Biological sampling procedures

7.5.1 Volume of blood

The total volume of blood that will be drawn from each patient in this study during screening, treatment and follow-up is shown in the Laboratory Manual.

7.5.2 Handling, storage and destruction of biological samples

The samples will be used up, or disposed of after analyses or retained for further use as described below.

Any pharmacokinetic sample remaining after analysis for ceralasertib and its metabolites may be used for biomarker analyses. These analyses are for AstraZeneca use only and will not be included in the Clinical Study Report.

Biological samples for future research will be retained at Sponsor or its designee for a maximum of 15 years following the finalisation of the Clinical Study Report. The results from future analysis will not be reported in the Clinical Study Report but separately in a Clinical Study Report Addendum, Scientific Report or Scientific Publication.

7.5.2.1 Pharmacokinetic samples

Incurred sample reproducibility analysis, if any, will be performed alongside the bioanalysis of the test samples and reported in a separate bioanalytical report.

The results from the investigation will not be reported in the Clinical Study Report but separately in a bioanalytical report.

7.5.2.2 Samples for exploratory research

Details of sample collection, processing, shipping and storage will be described in the Laboratory Manual.

Each sample for exploratory research will be identified with the study number and patient enrolment number. In this way exploratory biomarker and genetic data may be correlated with clinical data, samples destroyed in the case of withdrawal of consent and regulatory audit enabled.

Where genetic analysis will be undertaken, no personal details identifying the individual will be available to any person (AstraZeneca employee or contract laboratory staff) working with the DNA.

7.5.3 Labelling and shipment of biohazard samples

The Principal Investigator ensures that samples are labelled and shipped in accordance with the Laboratory Manual and the Biological Substance, Category B (materials containing or suspected to contain infectious substances that do not meet Category A criteria), see Appendix D of this Clinical Study Protocol 'IATA 6.2 Guidance Document'.

Any samples identified as Infectious Category A materials are not shipped and no further samples taken from the patient unless agreed with AstraZeneca and appropriate labelling, shipment and containment provisions are approved.

All archival tumour samples should be shipped at ambient temperature as per the Laboratory Manual to the AstraZeneca designated central Contract Research Organisation. Please refer to section 6.6.5 of the master protocol for details about chain of custody of biological samples.

7.5.4 Withdrawal of informed consent for donated biological samples

If a patient withdraws consent to the use of voluntarily donated biological samples, then the samples will be disposed of/destroyed, and the action documented. If samples are already analysed, AstraZeneca is not obliged to destroy the results of this research.

As collection of these biological samples is a voluntary part of the study then the patient may continue in the study.

The Principal Investigator:

- Ensures AstraZeneca is notified immediately of the patient's withdrawal of informed consent to the use of donated biological samples
- Ensures that biological samples from that patient, if stored at the study site, are immediately identified, disposed of/destroyed, and the action documented
- Ensures the laboratory(ies) holding the samples is/are informed about the withdrawn consent immediately and that samples are disposed of/destroyed, the action documented and the signed document returned to the study site
- Ensures that the patient and AstraZeneca are informed about the sample disposal

AstraZeneca ensures the central laboratory(ies) holding the samples is/are informed about the withdrawn consent immediately and that samples are disposed of/destroyed, the action documented and the document returned to the study site.

8. SAFETY REPORTING AND MEDICAL MANAGEMENT

Please refer to [Section 7](#) of the master protocol for details of reporting AEs, SAEs, AEs of special interest, paternal exposure, and management of investigational product (IP) related toxicities applicable to all arms in the study. Additional details for reporting AE, SAEs, AEs of special interest, paternal exposure, and management of IP related toxicities applicable to Arm C are described below.

8.1 Reporting of adverse events

8.1.1 Time period for collection of adverse events

AEs and SAEs will be recorded from the time of informed consent, throughout the treatment period, and including the follow-up period (the follow-up period is 30 days after the last dose of study treatment of ceralasertib and olaparib). SAEs occurring in the follow-up period should be reported in the usual manner.

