2.4.4.2 Adverse events of special interest for olaparib

Myelodysplastic syndrome/acute myeloid leukaemia

The incidence of MDS/AML in patients treated in clinical trials with olaparib monotherapy, including long-term survival follow-up, was <1.5% and the majority of events had a fatal outcome. All patients had potential contributing factors for the development of MDS/AML, having received previous chemotherapy with platinum agents. Many had also received other DNA damaging treatments. The majority of reports were in germline BRCA mutation carriers and some of the patients had a history of previous cancer or of bone marrow dysplasia. If MDS and/or AML are confirmed while on treatment with olaparib, it is recommended that olaparib should be discontinued and the patient be treated appropriately.

New Primary Malignancies other than MDS/AML

New primary malignancies have been reported in <1% of patients. There were other contributing factors/potential alternative explanations for the development of the new primary malignancy in all cases, including documented BRCA mutation, treatment with radiotherapy and extensive previous chemotherapy including carboplatin, taxanes, anthracyclines and other alkylating and DNA damaging agents.

Pneumonitis

Pneumonitis has been reported in <1.0% patients treated with olaparib monotherapy in clinical studies. Reports of pneumonitis had no consistent clinical pattern and were confounded by a number of pre-disposing factors (cancer and/or metastases in lungs, underlying pulmonary disease, smoking history, and/or previous chemotherapy and radiotherapy). When olaparib was used in clinical studies in combination with other therapies there have been events with a fatal outcome. If patients present with new or worsening respiratory symptoms such as dyspnoea, cough and fever, or an abnormal chest radiologic finding is observed, olaparib treatment should be interrupted and prompt investigation initiated. If pneumonitis is confirmed, olaparib treatment should be discontinued and the patient treated appropriately.

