2.5.2.2 Olaparib

Adverse laboratory findings and/or clinical diagnoses considered to be associated with administration of olaparib monotherapy include haematological effects (anaemia, neutropenia, lymphopenia, thrombocytopenia, MCV elevation and increase in blood creatinine), nausea and vomiting, decreased appetite, diarrhoea, dyspepsia, stomatitis, upper abdominal pain, dysgeusia, fatigue (including asthenia), headache and dizziness. Most of these events were generally mild or moderate in intensity.

In a relatively small number of patients, pneumonitis, MDS/AML and new primary malignancies have been observed. Evidence from across the development programme for olaparib does not support a conclusion that there is a causal relationship between olaparib and these events. These are important potential risks for olaparib and are being kept under close surveillance.

See the latest version of the IB for further information.

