8.1.4 Post study events

After the patient has been permanently withdrawn from the study, there is no obligation for the Investigator to actively report information on new AEs or SAEs occurring in former study patients after the arm designated number of days, or 30 day safety follow-up period. However, if an Investigator learns of any SAEs, including death, at any time after the patient has been permanently withdrawn from the study, and he/she considers there is a reasonable possibility that the event is related to the study treatment, the Investigator should notify AstraZeneca, Patient Safety, or its representative.

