10.1 Adverse events

AEs observed up to 30 days following discontinuation of study treatment or until the initiation of the first subsequent therapy following discontinuation of treatment (whichever occurs first) will be used for the reporting of AE summary tables. This will more accurately depict AEs attributable to study treatment only, as a number of AEs up to 30 days following discontinuation of the study treatment are likely to be attributable to subsequent therapy.

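### After day 30, Arm C schedules no question about MDS/AML or new primary malignancy, so late cases of these olaparib special-interest events may be under-ascertained

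*Protocol*

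**What the plan says.** **Collection window.** Appendix C section 8.1.1 records AEs and SAEs from consent through follow-up, where "the follow-up period is 30 days after the last dose of study treatment of ceralasertib and olaparib". In Appendix C Table 3 the adverse-event row stops at the 30-day visit, and the later column for progression and survival has no adverse-event entry. Footnote n schedules survival contacts monthly for three months and then every two months. It mentions survival only.

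**Events of special interest.** Appendix C section 2.4.4.2 lists MDS/AML and new primary malignancies. For MDS/AML on olaparib monotherapy the incidence, "including long-term survival follow-up, was <1.5% and the majority of events had a fatal outcome". For the other: "New primary malignancies have been reported in <1% of patients", with no statement about follow-up or fatality. Section 2.5.2.2 adds, of pneumonitis, MDS/AML and new primary malignancies: "These are important potential risks for olaparib and are being kept under close surveillance".

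**After the window.** Under section 8.1.4, once a patient is permanently withdrawn, "there is no obligation for the Investigator to actively report information on new AEs or SAEs occurring in former study patients" after the 30-day period. A passive route stays open "if an Investigator learns of any SAEs, including death, at any time after the patient has been permanently withdrawn from the study", provided the investigator sees a reasonable possibility of a link to study treatment.

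**Reporting.** Section 10.1 builds the AE summary tables from "AEs observed up to 30 days following discontinuation of study treatment" or until subsequent therapy starts, if sooner. Master protocol section 9.4.2.1 puts later events in a separate listing.

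**The concern.** The protocol's own description of MDS/AML depends on looking well beyond the end of treatment, yet Arm C stops asking at day 30. The sites go on contacting these patients but are given no prompt about the two delayed events that the appendix singles out.

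The contrast with the other arms sharpens this. Arm B has the same 30-day window (Appendix B section 7.1.1), but Appendix B Table 1 footnote s requires both survival and adverse-event assessment on the same later contact schedule. Arm A collects for 90 days and says that a later event attributed to late-onset toxicity is still reported (Appendix A section 7.1). Appendix C section 8 has neither provision, and no reason is given.

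At stake is the completeness of late safety data for olaparib given with a second agent acting on the DNA damage response. Efficacy analyses, sample size and decision rules are unaffected.

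**Working it through.** **1. What could pick up a case after day 30**

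| Place | What it covers | What it depends on |
|---|---|---|
| Master 4.9.2 | drug- or procedure-related SAEs until the follow-up period ends or the patient is permanently withdrawn | relatedness, and the meaning of follow-up period |
| Master 7.3.2.1 and Appendix C 8.1.4 | SAEs at any time after permanent withdrawal | investigator happens to learn of it and judges it possibly related |
| Master 7.3.11 | later deaths on the Statement of Death page; SAE if due to late-onset toxicity | death has occurred; relatedness for SAE status |
| Master 7.3.10 | a new cancer is an SAE | no scheduled question finds it |
| Appendix C 8.4.2.3 | confirmed MDS/AML is an SAE with full reports | sits under toxicities on study treatment, though the sentence has no time limit |
| Master 9.4.2.1 | listing of post-window AEs | the event having been recorded |

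None of these asks the patient or the treating physician about the two events. Three depend on relatedness for SAE reporting.

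**2. How the relatedness condition may act.** All Arm C patients have had platinum (inclusion criterion 5). Section 2.4.4.2 cites prior platinum as a potential contributing factor for MDS/AML. Section 2.5.2.2 says the evidence does not support a causal link. Appendix H says that an event with limited information is likely to be assessed as not related. Together these make a causality-dependent route a weak net, though the documents do not say how often it would fail.

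**3. An unclear term.** Master 4.9.2 runs capture of related SAEs to the end of the follow-up period after discontinuation. Appendix C 8.1.1 sets that period at 30 days. Section 8.1.4 attaches its rule to patients permanently withdrawn, whereas patients in survival follow-up remain in the study under master 4.9.2. The duty towards a patient alive and in survival follow-up at day 60, say, cannot be read off with certainty.

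**4. Scale.** The plan gives no figure of its own for late events, so there is none to reproduce.

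Inputs: MDS/AML rate p below 0.015 and new primary malignancy rate below 0.010 (Appendix C 2.4.4.2); n = 20 (Appendix C section 3); master maximum n = 40 (section 9.2); survival s of 37% at 6 months and 9% at 12 months, from the topotecan meta-analysis in master section 2.3.

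Expected cases = n × p. Chance of at least one = 1 − (1 − p)^n.

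- MDS/AML at the ceiling, n = 20: 20 × 0.015 = 0.30 expected; 1 − 0.985^20 = 26.1%.
- MDS/AML at the ceiling, n = 40: 0.60 expected; 1 − 0.985^40 = 45.4%.
- New primary malignancy at the ceiling: n = 20, 0.20 expected, 18.2%; n = 40, 0.40 expected, 33.1%.

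Scenarios in which only longer survivors are at risk of MDS/AML, using 1 − (1 − p × s)^n:

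- Alive at 6 months: p × s = 0.015 × 0.37 = 0.00555. Chance 10.5% with 20 patients, 20.0% with 40.
- Alive at 12 months: p × s = 0.015 × 0.09 = 0.00135. Chance 2.7% with 20 patients, 5.3% with 40.

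Fewer than one case of either type is expected in every scenario.

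**The case against.** A reader might infer that late cases would simply go unreported. The documents do not support that: the routes tabulated above remain open, the master safety sections apply to Arm C, and post-window events have a listing. Only active questioning is missing. That correction stands in full.

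Three further limits also stand.

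- The long-term follow-up basis and the mostly fatal outcome are stated for MDS/AML only. They cannot be carried over to new primary malignancies.
- The surveillance sentence in section 2.5.2.2 follows a statement about evidence across the development programme. It does not promise long-term questioning in this arm, so the Arm C schedule does not break it.
- The 26% and 45% are ceilings for any case at any time, including cases on treatment or within 30 days, which are already captured. They are not chances of a missed case. The protocol gives no latency, so the share falling after day 30 is unknown. The 40-patient figure also exceeds the 20 planned in Appendix C.

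It is also fair to say that cutting the AE summaries at 30 days is a reasoned choice, explained in section 10.1. With at most a stray case expected, a listing serves as well as a separate summary table.

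None of this answers the contrast with Arm B, or explains why contacts that already take place omit the question.

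**Conclusion.** The point holds as a minor weakness in ascertainment. After day 30 Arm C relies on passive reporting, mostly filtered by causality, for two events that its own appendix names as being of special interest. Late cases may be under-ascertained; they are not shut out.

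The practical size is small. With the 20 patients planned, the chance of any MDS/AML case is at most 26%, and about 10.5% or 2.7% if only 6- or 12-month survivors are at risk. Those two lower figures assume that the meta-analysis survival rates apply to Arm C and that survivors carry the full 1.5% rate. All the figures treat a rate stated for olaparib monotherapy as applying to the combination, which the documents neither confirm nor exclude. The change is worth making because it is cheap, not because many events are likely.

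**What to change.** - In Appendix C section 8.1.1 and Table 3 footnote n, add a question on MDS/AML and new primary malignancy at the existing survival contacts.
- State that any such case is reported as an SAE regardless of time since last dose or judged causality, and appears in the post-window listing already planned in master section 9.4.2.1. A separate summary table is not needed.
- Reconcile the meaning of follow-up period across master section 4.9.2 and Appendix C sections 8.1.1 and 8.1.4, saying which duties apply to patients still in survival follow-up and which to those permanently withdrawn.

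Cost: one extra question per contact, with no new visit, test or staff, and no change to any dose or treatment rule. It does need a protocol amendment, with ethics and, where applicable, regulatory approval under master section 11.5, so it is best bundled with other changes.

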8.1.2 Follow-up of unresolved adverse events

Please refer to [Section 7.3.2](#) of the master protocol for details of follow-up of unresolved adverse events.

8.1.3 Reporting of serious adverse events

Please refer to Section 7.4 of the master protocol for details of reporting of serious adverse events.

8.1.4 Post study events

After the patient has been permanently withdrawn from the study, there is no obligation for the Investigator to actively report information on new AEs or SAEs occurring in former study patients after the arm designated number of days, or 30 day safety follow-up period. However, if an Investigator learns of any SAEs, including death, at any time after the patient has been permanently withdrawn from the study, and he/she considers there is a reasonable possibility that the event is related to the study treatment, the Investigator should notify AstraZeneca, Patient Safety, or its representative.

8.2 Pregnancy

8.2.1 Maternal exposure

If a patient becomes pregnant during the course of the study treatment should be discontinued immediately. Pregnancy itself is not regarded as an AE event unless there is a suspicion that the study treatment under investigation may have interfered with the effectiveness of a contraceptive medication. Congenital abnormalities/birth defects and spontaneous miscarriages should be reported and handled as SAEs. Elective abortions without complications should not be handled as AEs. The outcome of all pregnancies (spontaneous miscarriage, elective termination, ectopic pregnancy, normal birth, or congenital abnormality) should be followed up and documented even if the patient was discontinued from the study.

If any pregnancy occurs in the course of the study, the Investigator or other study center personnel must inform the appropriate AstraZeneca representatives within 1 calendar day (ie, immediately but no later than 24 hours of when he or she becomes aware of it).

The designated AstraZeneca representative works with the Investigator to ensure that all relevant information is provided to the AstraZeneca Patient Safety data entry site within 1 or 5 calendar days for SAEs, and within 30 days for all other pregnancies.

The same timelines apply when outcome information is available.

8.2.2 Paternal exposure

Pregnancy of the patient's partner is not considered to be an AE. However, the outcome of all pregnancies (spontaneous miscarriage, elective termination, ectopic pregnancy, normal birth, or congenital abnormality) should be followed up and documented if possible. To capture information about a pregnancy from the partner of a male patient, consent must be obtained from the male patient's partner to collect information related to the pregnancy and outcome; the male patient should not be asked to provide this information.

8.3 Overdose of either olaparib or ceralasertib

There is no specific treatment in the event of olaparib or ceralasertib overdose, and no symptoms of overdose are established. In the event of overdose, physicians should follow general supportive measures and should treat symptomatically.

8.4 Dose modifications and management of investigational product related toxicities

Guidelines for the management of hematological and non-hematological AEs for ceralasertib and olaparib are described below. Given the aggressive nature of relapsed or refractory SCLC and the lack of an effective standard of care in this clinical setting, doses of ceralasertib and olaparib will be modified by cycle (see Section 2.1 of the CSP). Subsequent cycles will be further adjusted to patient tolerance and investigator judgement.

Toxicity will be assessed utilizing the NCI Common Terminology Criteria for Adverse Event (CTCAE) version 4.03 unless otherwise specified. Every effort should be made to administer trial treatment at the planned dose and schedule. However, patients experiencing toxicities related to the trial treatment may have their dose modified as outlined in this section.

Any toxicity observed during the course of the study could be managed by interruption of study treatment or dose reductions, and initiation of supportive care as deemed appropriate by the investigator. In the event that a patient has not recovered sufficiently to enable the next chemotherapy cycle to start, then the cycle should be delayed until the toxicity has recovered sufficiently to allow further dosage. The maximum cycle delay is permitted in 28 days. Repeat dose interruptions are allowed as required, for a maximum of 28 days on each occasion. Any patient requiring a toxicity related dose delay of more than 28 days from the intended day of the next scheduled dose must be discontinued from the study unless there is approval from the Study Physician for the patient to continue.

If Day 1 treatment with either ceralasertib or olaparib is interrupted, then both study medications will be delayed until the combination can be resumed. Dose adjustments will be based on the organ system exhibiting the greatest degree of toxicity.

